### 5.3.5 Laboratory Data

Laboratory data will be summarized for each assessment visit using descriptive statistics of absolute values and change from baseline values. In addition, the frequency of patients with abnormal laboratory values will be summarized.

#### 5.3.6 Vital Signs

Vital signs assessments include systolic blood pressure, diastolic blood pressure, and pulse rate measured throughout the study. Vital sign measurements will be summarized for each assessment visit using descriptive statistics of absolute values and change from baseline values. In addition, the frequency of patients with abnormal results will be summarized.

#### 5.3.7 ECGs

ECG data will be summarized by previous treatment group and participation / nonparticipation in the OLE part of the parent studies for each assessment visit using descriptive statistics of absolute values and change from baseline values for the following parameters:

- Heart rate
- QRS duration
- RR interval
- PR interval

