1.3.2 Safety Overview

Nonclinical characterization of gantenerumab did not show relevant safety findings. No differences between gantenerumab and placebo groups have been observed in laboratory parameters, physical and neurologic examinations, vital signs, or ECG parameters.

The identified risks of gantenerumab treatment are ARIAs and ISRs. Safety data and MRI findings are continuously monitored in all ongoing studies, and no new safety signals have been identified.

The Gantenerumab Investigator's Brochure includes a summary of safety data with gantenerumab SC in participants with AD from Studies WN25203 and WN28745 as well as from Phase I studies with gantenerumab SC and IV.

Providing participants who complete study treatment in the pivotal Studies WN22992 and WN39658 with an opportunity to extend or initiate treatment with open-label gantenerumab in Study WN42171 will allow the collection of more information on the long-term safety and tolerability of gantenerumab in AD. It will also provide more information on its efficacy in the context of long-term exposure. Furthermore, the OLE will increase the overall number of participants exposed to gantenerumab and participant-years of exposure, thus increasing understanding of the safety and efficacy profiles.

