- Blood, plasma, serum, and CSF samples collected for biomarker research and biomarker assay development will be destroyed no later than 5 years after the final Clinical Study Report has been completed. However, the storage period will be in accordance with the IRB/EC-approved Informed Consent Form and applicable laws (e.g., health authority requirements)

When a participant withdraws from the study, samples collected prior to the date of withdrawal may still be analyzed, unless the participant specifically requests that the samples be destroyed or local laws require destruction of the samples. However, if samples have been tested prior to withdrawal, results from those tests will remain as part of the overall research data.

Data arising from sample analysis, including data on genomic variants, will be subject to the confidentiality standards described in Section 8.4.

Given the complexity and exploratory nature of exploratory biomarker analyses, data derived from these analyses will generally not be provided to study investigators or participants unless required by law. The aggregate results of any conducted research will be available in accordance with the effective Sponsor policy on study data publication.

4.5.8 Electrocardiograms

Single 12-lead ECG recordings will be obtained at specified timepoints, as outlined in the schedule of activities (see Appendix 1), and may be obtained at unscheduled timepoints as indicated.

The centrally provided electrocardiograph machine should record the following: heart rate, QRS duration, and RR, PR, and QT intervals and transferred to the Sponsor database from the core laboratory.

At the OLE Day 1 visit or at the visit of the first study drug administration in Study WN42171, ECG does not have to be repeated if the last ECG performed in the parent studies WN29922 or WN39658 occurred within 4 weeks.

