### 2. STATISTICAL HYPOTHESES

All analyses provided in this document are descriptive, thus no statistical hypothesis will be tested in these analyses.

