### 3. SAMPLE SIZE DETERMINATION

The sample size will be determined by the number of participants who complete the parent studies (GRADUATE I and GRADUATE II) and enroll in this study. The sample size is expected to be no more than approximately 2032 participants.

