#### 5.3 PRIMARY ENDPOINTS ANALYSIS

### 5.3.1 Definition of Primary Endpoints

The primary objective for this study is to evaluate the safety and tolerability of long-term gantenerumab administered by SC injection on the basis of adverse events (AEs), physical examinations, vital signs, ECGs, laboratory tests, C-SSRS, ARIA-E and ARIA-H, ISRs, treatment discontinuations for AEs, and incidence of AEs of special interest.

The corresponding primary endpoints are:

- Nature, frequency, severity, timing, and outcomes of adverse events and serious adverse events
- Physical examinations (including neurologic systems), vital signs, ECG, laboratory tests, and Columbia-Suicide Severity Rating Scale (C-SSRS)
- Nature, frequency, severity, and timing of ARIA-E and ARIA-H

- Nature, frequency, severity, timing, and outcomes of ISRs
- Incidence of treatment discontinuations for adverse events
- Incidence of adverse events of special interest

The analytical approaches are described in pertinent subsection for each endpoint below.

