#### QT interval

In addition, ECG overall interpretations will be summarized by previous treatment group, participation / non-participation in the OLE part of the parent studies and visit.

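### SAP 5.3.7 summarises QT only without rate correction, so a heart-rate shift between the few scheduled ECGs can mimic or mask a change in repolarisation

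*SAP*

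**What the plan says.** SAP 5.3.1 lists ECG among the primary safety endpoints: "Physical examinations (including neurologic systems), vital signs, ECG, laboratory tests" and C-SSRS.

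For each assessment visit, by previous treatment group and parent-OLE participation, SAP 5.3.7 plans "descriptive statistics of absolute values and change from baseline values for the following parameters". The list has five entries: heart rate, QRS duration, RR interval, PR interval and QT interval. One further summary follows: "In addition, ECG overall interpretations will be summarized by previous treatment group", OLE participation and visit.

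Protocol 4.5.8 has the machine record the same five quantities: "heart rate, QRS duration, and RR, PR, and QT intervals". On replication it says: "Single 12-lead ECG recordings will be obtained at specified timepoints". Protocol 6.4 says ECG is summarised descriptively and leaves methods to the SAP. SAP Appendix 1 has nothing on ECG. Neither document names a corrected QT, a correction formula or a count of QT outliers.

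Scheduled ECGs are few (Protocol Appendix 1). Participants titrated in this study have them at OLE Day 1, Week 104 and Week 220. Those coming from the parent OLE have them at Week 36, Week 104 and Week 220. Early termination and unscheduled visits can add more.

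**The concern.** QT depends on the RR interval, and the plan's only QT measure takes no account of it. A change from baseline in raw QT is therefore the sum of a rate effect and a repolarisation effect, and the tables give no way to separate the two for any participant.

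The spacing of the recordings makes this relevant. For a participant titrated in this study, the change at Week 104 compares two single tracings two years apart. Protocol 4.5.8 asks sites to avoid things that could alter heart rate around the recording, which controls the session but not drift between visits. Protocol 4.4.1 allows medication to be added or changed for adverse events or AD progression.

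At stake is how the ECG part of the primary safety summary can be read, in either direction. An apparent QT change may be only rate, and an apparently flat QT is not by itself reassuring. ECG data are also in the planned interim analyses (SAP 5.8.1), the first of which is meant to support a potential filing. Unlike the laboratory and vital-sign sections (SAP 5.3.5 and 5.3.6), the ECG section does not plan a frequency of abnormal values for each parameter, so a participant with a long rate-adjusted QT would not be tabulated as such.

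**Working it through.** **The plan's own figure.** There is none to reproduce. The ECG analysis is descriptive (SAP 2: "thus no statistical hypothesis will be tested in these analyses"), with no QT threshold, margin or power statement.

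**Inputs.** QT and RR are both recorded at every ECG (Protocol 4.5.8). Neither document gives heart-rate or QT values, so those below are assumptions.

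**Formula.** Fridericia: QTcF = QT / RR^(1/3), with RR = 60 / heart rate in seconds. Hence QT = QTcF × (60 / heart rate)^(1/3).

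**Rate shift, no true effect (QTcF fixed at 400 ms).**

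| Heart rate (bpm) | Raw QT (ms) | Change from 60 bpm (ms) |
|---|---|---|
| 60 | 400.0 | 0 |
| 65 | 389.5 | -10.5 |
| 70 | 380.0 | -20.0 |

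A fall in rate reverses the sign: 65 to 60 bpm gives +10.5 ms and 70 to 60 bpm gives +20.0 ms. With QTcF fixed at 440 ms instead, 60 to 65 bpm gives -11.6 ms and 60 to 70 bpm gives -22.0 ms.

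**True effect, masked.** Suppose QTcF rises from 420 to 430 ms while heart rate goes from 65 to 70 bpm.
- Before: 420 × (60/65)^(1/3) = 408.9 ms.
- After: 430 × (60/70)^(1/3) = 408.5 ms.
- Raw change: about -0.5 ms, against a true change of +10 ms.

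The rate that would cancel the 10 ms exactly is 65 × (430/420)^3 = 69.8 bpm.

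**Does the result depend on the cube-root form?** Take a true QTc of 400 ms and 60 to 65 bpm.
- Linear form, QT = QTc - 154 × (1 - RR): raw QT moves by -11.8 ms. QTcF computed on those data would be 388.2 / (60/65)^(1/3), or 398.6 ms, leaving a residual of about -1.4 ms.
- Square-root form, QT = QTc × RR^(1/2): raw QT moves by -15.7 ms. QTcF would be 400 × (60/65)^(1/6) = 394.7 ms, leaving about -5.3 ms.

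So the raw shift is roughly 10 to 16 ms for 5 bpm under all three forms. QTcF removes all of it if the cube-root form is right, most of it under the linear form, and about two thirds under the square-root form.

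**The case against.** The strongest reply is that QT does not stand alone. Heart rate and RR are summarised beside it at every visit, so a group-level rate shift would be visible. Overall interpretations are tabulated, investigators must review and sign every tracing (Protocol 4.5.8), and an ECG deterioration that brings symptoms or changes treatment is an adverse event (Protocol 5.2.1). No decision rule uses QT. The background is also reassuring; Protocol 1.3.2 states: "No differences between gantenerumab and placebo groups have been observed in laboratory parameters, physical and neurologic examinations, vital signs, or ECG parameters".

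Most of this stands, and it limits the weight of the point. It does not remove it. Separate means for rate and QT do not adjust QT within a participant or show whose rate-adjusted interval is long. Interpretations and adverse event reports catch clinically evident abnormalities, not a modest systematic change.

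It can also be said that the illustration assumes its rate shifts. That is correct: nothing in either document says that mean heart rate will move by 5 or 10 bpm. Scheduled ECGs are also sparse. For those who complete treatment, Week 220 falls 14 weeks after the final dose at Week 206, so after Week 36 the only scheduled on-treatment ECG is at Week 104. There is no dense QT series for a rate drift to distort.

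Finally, SAP 1 leaves datasets and output layouts to a separate data analysis plan, where a QTcF variable could appear. But SAP 5.3.7 is where the summarised parameters are chosen, and QTcF is not among them.

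**Conclusion.** The point holds in conditional form. The only planned QT measure is uncorrected, so its change from baseline can mimic or mask a repolarisation change if heart rate shifts between recordings. Under the assumed values the distortion is about 10 ms for 5 bpm and 20 ms for 10 bpm, and a rise of about 5 bpm is enough to hide a true 10 ms prolongation.

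Three stronger readings are tempting, and the documents do not support them:
- A reader might infer that the QT summary will be misleading. That needs a heart-rate shift, which the documents neither report nor predict.
- A reader might infer that QTcF would show a drug effect. The study is open-label and non-randomised, every participant receives gantenerumab, and recordings are single. A QTcF change from baseline would still mix drug with ageing, illness and concomitant medication.
- A reader might infer a suspected QT risk. The protocol reports no ECG difference from placebo and names only ARIA and injection-site reactions as identified risks.

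Priority is low to moderate. The analysis is descriptive and no ECG signal has been reported, but ECG is a primary safety endpoint and the improvement uses data already in hand.

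**What to change.** In SAP 5.3.7, add QTcF = QT / (RR in seconds)^(1/3), derived for each ECG from its own QT and RR. Summarise its absolute value and change from baseline by visit, in the same participant groups, as the main QT parameter. Keep raw QT, heart rate and RR as supportive.

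If categorical QTcF counts are added, state the absolute and change thresholds in the SAP itself, since neither document contains any. A sentence noting that the change from baseline is uncontrolled would guard against over-reading it.

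The cost is a SAP edit, one derived variable and one table. No new data and no protocol amendment are needed, because Protocol 4.5.8 already collects both inputs and Protocol 6.4 leaves the methods to the SAP.

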#### QT interval

In addition, ECG overall interpretations will be summarized by previous treatment group, participation / non-participation in the OLE part of the parent studies and visit.

### 5.3.8 Columbia-Suicide Severity Rating Scale (C-SSRS)

The C-SSRS is a tool used to assess the lifetime suicidality of a participant (C-SSRS at baseline) as well as any new instances of suicidality (C-SSRS since last visit). The structured interview prompts recollection of suicidal ideation, including the intensity of the ideation, behavior, and attempts with actual or potential lethality.

Suicidal ideation, suicidal behavior, and self-injurious behavior without suicidal intent will be summarized by previous treatment group and participation / non-participation in the OLE part of the parent studies. In addition, change from baseline to worst post-baseline assessment in suicidality categories will be summarized by previous treatment group and participation / non-participation in the OLE part of the parent studies.

### 5.4 SECONDARY ENDPOINTS ANALYSES

According to the study protocol, section 6.5, the secondary efficacy analyses are planned to use all enrolled participants to investigate both the long-term efficacy and potential disease modifying effect of long-term gantenerumab. However, all analyses in this SAP will be restricted to efficacy endpoints collected under this study or during the OLE part of the parent studies and will be purely descriptive. No estimands will be defined.

Analyses of long-term effect of the study drug (across the double-blind and open label phases from the parent Study [GRADUATE I or GRADUATE II]) as well as efficacy analyses of delayed start of treatment are not subject to this SAP and will be described elsewhere.

### 5.4.1 Secondary Efficacy Endpoints

The secondary objective for this study is to evaluate the efficacy of long-term gantenerumab administered by SC injection on the basis of change over time in cognition, function, and other outcomes as measured by the following:

- Clinical Dementia Rating (CDR)
- Mini-Mental State Examination (MMSE)
- Alzheimer Disease Assessment Scale-Cognition, Subscale 11 (ADAS-Cog11) and Alzheimer Disease Assessment Scale-Cognition, Subscale 13 (ADAS-Cog13)
- Verbal Fluency Task
- Coding
- Functional Activities Questionnaire (FAQ)
- Alzheimer Disease Cooperative Study Group-Activities of Daily Living (ADCS-ADL)

Descriptive statistics will be provided for each of these endpoints, summarizing absolute values and change from baseline for each assessment time point by previous treatment group and participation / non-participation in the OLE part of the parent studies.

#### 5.4.1.1 Clinical Dementia Rating

The CDR-Global Score (CDR-GS) characterizes a participant's level of impairment according to the following categories: 0 (normal), 0.5 (very mild dementia), 1 (mild dementia), 2 (moderate dementia), and 3 (severe dementia). The CDR-Sum of Boxes (CDR-SOB) score is a detailed quantitative general index that provides more information than the CDR-GS in participants with mild dementia (Berg 1988; Morris et al. 2001, O'Bryant et al. 2010) and is scored from 0 to 18 with higher scores indicating greater impairment. The CDR characterizes six domains: memory, orientation, judgment and problem solving, community affairs, home and hobbies, and personal care. The necessary information to make each rating is obtained through a semi-structured interview with the participant and a reliable informant or collateral source (e.g., a caregiver).

Descriptive statistics will be provided for the CDR-SOB and the CDR-GS.

#### 5.4.1.2 MMSE

The MMSE is a set of standardized questions used to evaluate possible cognitive impairment and help stage the severity level of this impairment (Folstein et al. 1975). The questions target six areas: orientation, registration, attention, short-term recall, language, and constructional praxis/visuospatial abilities. The MMSE is a participant-based assessment. The score ranges from 0 to 30, with lower values indicating a greater impairment.

#### 5.4.1.3 ADAS-Cog11 and ADAS-Cog13

The ADAS-Cog is the most frequently used scale to assess cognition in clinical trials for mild to moderate AD dementia (Rozzini et al. 2007; Connor and Sabbagh 2008; Ihl et al. 2012). More specifically, the ADAS-Cog is a participant-based assessment that measures learning and memory, language production, language comprehension, constructional praxis, ideational praxis, and orientation. The modified version will be used; it has 13 items and includes the addition of delayed word recall and a number of cancellation subtests, as well as use of only one trial for word recognition (Mohs et al. 1997). Equivalent alternate forms of the word recall, word recognition, and number cancellation subtests will be used in successive test administrations. The ADAS-Cog 11 and 13 will be used in this study. Individual item scores are based on errors and generally range from 1 to 5, although some items have smaller or larger score ranges. The ADAS-Cog 13 total score ranges from 0 to 85, with higher scores reflecting greater impairment. It takes approximately 45 minutes to administer the ADAS-Cog 13.

### 5.4.1.4 Verbal Fluency Task

The category verbal fluency (e.g., animals) is a participant-based assessment that measures speed and flexibility of verbal thought. Verbal fluency tests are sensitive tools for detecting dementia (Pasquier et al. 1995; Lezak et al. 2004) and for monitoring decline over time (Clark et al. 2009).

### 5.4.1.5 Coding

The Coding, also called Digit Symbol Substitution Test (or DSST), is a subtest from the Wechsler Adult Intelligence Scale-Fourth Edition (WAIS-IV; Wechsler 2008). The Coding is a participant-based assessment that measures speed of processing and associative memory. The test is known to be sensitive to disease progression (Lezak et al. 2004). The 120-second version of the test will be used in this study.

#### 5.4.1.6 FAQ

The FAQ (Pfeffer et al. 1982) is an informant-based measure of functional abilities. Informants provide performance ratings of the target person on ten complex higher-order activities. The FAQ is a 30-point scale, the higher the score the worse the performance.

#### 5.4.1.7 ADCS-ADL

The ADCS-ADL (Galasko et al. 1997) is the scale most widely used to assess functional outcome in participants with AD (Vellas et al. 2008). The ADCS-ADL is a 23-item informant-based questionnaire that covers both basic activities of daily living (ADL) (e.g., eating and toileting) and more complex ADL or instrumental ADL (e.g., using the telephone, managing finances, preparing a meal). It has a 4-week recall period. Total scores range from 0 to 78, with higher scores indicating better functioning.

### 5.5 EXPLORATORY ENDPOINTS ANALYSIS

The exploratory efficacy analyses will be based on the ITT analysis set and will be restricted to efficacy endpoints collected under this study or during the OLE part of the parent studies. Therefore, analyses of long-term effect of the study drug (across the double-blind and open label phases from the parent study [GRADUATE I or GRADUATE II]) are not subject to this SAP and will be described elsewhere.

### 5.5.1 Exploratory Efficacy Endpoints

The exploratory efficacy objective is to evaluate the efficacy of long-term gantenerumab administered by SC injection in terms of change over time in:

- Health-related quality of life, as assessed by the Quality of Life-Alzheimer's Disease (QoL-AD) scale
- Behavioral and neuropsychiatric symptoms of AD, as measured by the Neuropsychiatric Inventory Questionnaire (NPI-Q)
- Caregiver burden, as assessed by the Zarit Caregiver Interview for Alzheimer's Disease (ZCI-AD) scale

 Elements of resource utilization, as assessed by the Resource Utilization in Dementia-Lite (RUD-Lite)

The RUD-Lite will be used in this study for informing pharmacoeconomic evaluations and will be reported separately. For the other endpoints, descriptive statistics will be provided for these endpoints by previous treatment group, participation / nonparticipation in the OLE part of the parent studies and assessment time point.

#### 5.5.1.1 QoL-AD

The QoL-AD was developed to assess quality of life (QoL) in participants who have dementia (Logsdon et al. 1999, 2002). The QoL-AD consists of 13 items covering aspects of participants' relationships with friends and family, physical condition, mood, concerns about finances, and overall assessment of QoL. The total score is the sum of the 13 items and ranges from 13 to 52, with higher scores indicating better health-related QoL. In this study, the QoL-AD will be administered in a standardized, structured interview format to participants by investigative staff in order to gather participant responses about QoL. The caregiver will also complete the caregiver version of the questionnaire to enable proxy responses from the caregiver.

#### 5.5.1.2 NPI-Q

The NPI-Q (Kaufer et al. 2000) was developed to assess a wide range of behaviors encountered in patients with dementia, to provide a means of distinguishing severity of behavioral changes, and to facilitate rapid behavioral assessment through the use of screening questions. It is an informant-based instrument in which 12 behavioral domains are evaluated. The recall period is the past month, and severity scores range from 0 to 36, with higher scores indicating greater severity. The caregiver's distress portion of the scale will not be used in this study.

#### 5.5.1.3 ZCI-AD

ZCI-AD is a modified version of the Zarit Burden Interview, which was originally designed to reflect the stresses experienced by caregivers for people with dementia (Zarit and Zarit 1990). The modified version includes slight modifications in item and title wording (e.g., removal of "your relative" to refer directly to the participant, removal of "burden" from title) and the use of 11-point numerical rating scales. The ZCI-AD scale consists of 30 items and is completed by the caregiver without involvement from the site staff. It has a 4-week recall period.

